## 1.0 Research Design

### 1.1 Purpose/Specific Aims

The overall goal of this study is to explore the impact of HIV-associated distal sensory polyneuropathy on function, physical activity and pain pressure threshold, and conduct an interventional pilot trial of mindfulness meditation and transcutaneous nerve stimulation (TENS) to

mitigate symptoms and improve function in persons living with HIV-related distal sensory neuropathy (DSP).

#### A. Objectives

Aim 1. Determine if the presence of painful distal sensory polyneuropathy in the feet adversely affects function (gait and physical performance), physical activity, and pain pressure threshold in persons living with HIV (PLHIV). (From this point forward, protocol related to Aim 1 will be referred to as “cross-sectional phase”)

Aim 2. Determine the feasibility and effects of (1) mindfulness meditation or (2) transcutaneous nerve stimulation (TENS) on clinical and functional outcomes in persons with HIV-associated painful distal sensory polyneuropathy in the feet. (From this point forward, protocol related to Aim 1 will be referred to as “interventional phase”)

#### B. Hypotheses / Research Question(s)

Hypothesis for Aim 1 (cross-sectional phase): Temporal and spatial characteristics of gait, walking endurance, physical performance scores and pain pressure threshold scores will be worse, and physical activity will be lower, in those with DSP than in those without DSP.

Hypothesis for Aim 2 (interventional phase): There will be a beneficial effect on all clinical and functional outcomes in each of the 2 intervention groups (mindfulness meditation; TENS) compared to a standard care group.

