#### 1.4 Preliminary Data

There is no preliminary data; this is a new study. This interventional phase of this study will be used to generate data on the feasibility and effect sizes of the interventions that will be used for future projects.

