#### 1.5 Sample Size Justification

A sample of 80 participants will be enrolled in the cross sectional phase and 40 participants (those with DSP) will continue on to the interventional phase.

The target sample size of 72 (36 with DSP and 36 without DSP) for the cross sectional phase is adequate to explore of between group differences in gait, physical performance, physical activity, and pain pressure threshold variables. For the interventional phase, 36 participants (12 participants in each of the 3 groups) is adequate to demonstrate feasibility and determine effect sizes that can inform a future randomized controlled trial. The expected accrual rate is 90% (drop-out rate of <10%); thus, the number enrolled will be 80.

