## 6.0 Data Management Plan

### 6.1 Data Analysis

Cross-sectional phase: We will test for baseline differences between those with painful DSP and those without painful DSP for the set of variables using independent t-tests (or Mann-Whitney tests if distributions are non-normal). Differences between those with and without DSP on potential demographic or clinical confounders will be adjusted for statistically.

Interventional phase: Assuming normality of the outcome variables of interest, between group repeated measures analysis of variance will be used to evaluate differences within and between groups for each outcome separately. In the case of non-normal outcome variable distribution, we will consider transforming the measure to normalize. If normalization is not warranted, then within group changes will be tested using a Friedman's test and between group differences will be compared descriptively. Data will be analyzed using both per-protocol and intention-to-treat analyses in the case of dropouts.

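### The Aim 2 hypothesis and the separate unlabelled tests in 6.1 do not fit a 12-per-arm pilot meant to give feasibility and effect sizes

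*Combined protocol and SAP*

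**What the plan says.** The hypothesis for Aim 2 (1.1 B) reads "There will be a beneficial effect on all clinical and functional outcomes in each of the 2 intervention groups", against a standard care group. Aim 2 itself (1.1 A) is more modest: "Determine the feasibility and effects of (1) mindfulness meditation or (2) transcutaneous nerve stimulation (TENS) on clinical and functional outcomes". Section 1.4 says the interventional phase will "generate data on the feasibility and effect sizes of the interventions that will be used for future projects", and 1.5 calls 12 per arm enough to show feasibility and "determine effect sizes that can inform a future randomized controlled trial". Sections 1.1 and 6.4 D call this phase a pilot.

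Section 1.6 B lists the outcomes measured at Week 0 and Week 7 without ranking them. Under 6.1, repeated measures analysis of variance "will be used to evaluate differences within and between groups for each outcome separately". Where an outcome is not normal and is not transformed, within-group change goes to a Friedman test and "between group differences will be compared descriptively". Section 6.1 gives no alpha, sidedness, primary outcome, multiplicity rule, named pairwise contrast, confidence interval or statement that these tests are exploratory. The two contrasts with standard care can be inferred only from the hypothesis.

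**The concern.** The stated product of this phase is a set of effect sizes for planning a later trial. That calls for the difference in change between each active arm and standard care, with its uncertainty, for every outcome. As written, 6.1 produces significance tests. For non-normal outcomes it tests only change within each arm, which cannot separate treatment from regression to the mean or time. The hypothesis concerns benefit relative to standard care, so for those outcomes it is not tested, and no form of between-group estimate is laid down.

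With about 21 separate tests and no status attached to them, a few favourable p-values could be read as support for the hypothesis. The hypothesis also leaves out feasibility, which Aim 2 names first.

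**Working it through.** **The plan's own figure.** 12 × 3 = 36 completers. With 10% dropout, 36 / 0.90 = 40 enrolled in the interventional phase, and 72 / 0.90 = 80 overall. Both match 1.5. No alpha, power, effect size or precision target stands behind the 12 per arm, so nothing further can be reproduced.

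**Number of outcomes (1.6 B, with subscales from the instrument table in 1.9).**
- Gait: 6.
- 6-minute walk, SPPB, mid-thigh pull, pain pressure threshold, Actigraph, IPAQ-SF: 6.
- BPI: 2. MOS-HIV: 2. HADS: 2.
- Pain Catastrophizing Scale, Brief Resilience Scale, pain medication use: 3.
- Total: 6 + 6 + 2 + 2 + 2 + 3 = 21.

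The total is 20 if medication use is only described, and 22 if the two algometer sites are scored separately. Counting each instrument once gives 13.

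**Expected chance findings (ungated).** There are two contrasts per outcome, and at two-sided 5% each has a 0.025 chance of a favourable false positive. 21 × 2 × 0.025 = 1.05; 13 × 2 × 0.025 = 0.65. If pairwise tests are made only after a significant omnibus test, simulation gives about 0.5 and 0.3.

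**Chance of at least one favourable false positive.** Simulation of 20,000 trials per setting: 3 arms of 12, normal Week 0 to Week 7 changes, no true effect, equal correlation between outcomes, shared control arm. With two time points, the group-by-time test is a one-way analysis of variance on the change. Gated means the omnibus F test is also below 5%.

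| Outcomes | Correlation | Gated | Ungated | Median largest standardized difference |
|---|---|---|---|---|
| 21 | 0.3 | 27-28% | 46% | 0.81-0.82 |
| 21 | 0.5 | 21% | 35% | 0.72 |
| 21 | 0.7 | 15% | 25% | 0.6 |
| 13 | 0.3 | 19% | 34-35% | 0.72-0.73 |
| 13 | 0.5 | 15-16% | 28% | 0.65 |
| 13 | 0.7 | 11-12% | 20-21% | 0.54 |

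Ranges within a cell are repeat runs. The gated column is closer to 6.1, which specifies one analysis of variance per outcome and names no pairwise contrast. Both columns treat every outcome as tested between groups. Each outcome moved to the descriptive fallback removes tests, so for a given correlation the figures are upper bounds. Within-group tests are not counted.

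**Precision at 12 per arm.** The 95% CI half-width for a difference in mean change, in SDs of the change, is t(0.975, 22) × √(2/12) = 2.074 × 0.408 = 0.85.

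**Would a full correction work?** Bonferroni over 21 tests gives 0.05 / 21 = 0.0024 per test. The standardized difference detectable with 80% power at 12 per arm rises from 1.20 to 1.77. Correction is therefore not a useful remedy at this size; estimation is.

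**The case against.** The best defence is that this is a declared pilot. Sections 1.1, 1.4, 1.5 and 6.4 D all say so, and none promises confirmed efficacy. That stands, and 12 per arm is not criticised here. But the pilot label describes the design; it does not say how the outcome tests in 6.1 are to be read or that effect sizes will be reported with intervals.

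A reader might infer from the word all that Aim 2 succeeds only if every outcome is significant in both arms. The documents do not support this: the sentence states an expected direction, and no decision rule is attached to it. Nor is the wording in Aim 2 itself, which speaks of feasibility and effects.

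A reader might also infer that the most favourable effect size will be used to plan the next trial, and so inflate it. Nothing says this; the plan is silent on which outcome's effect size will be used. The last column of the table shows what noise alone can produce, not what the investigators intend.

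Finally, the error rates depend on an alpha and correlations that the documents do not give, and the ungated rates assume contrasts that 6.1 does not name. Both objections are fair, which is why the gated figures come first and ranges are shown. Some outcomes, such as stride width or medication use, may have no clear favourable direction or normal score, which again lowers the count.

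**Conclusion.** The concern holds as a mismatch between purpose and analysis. The hypothesis predicts benefit on every outcome in each arm, and 6.1 tests about 21 unranked outcomes separately without saying what the tests are for, while the phase is meant to deliver feasibility and effect sizes. For non-normal outcomes the mismatch is sharper, because only within-group change is tested. The chance of at least one favourable false positive is about 11-28% gated and 20-46% ungated. These figures rest on an assumed two-sided 5%, no true effect, correlation of 0.3 to 0.7 and 13 to 21 outcomes, and are upper bounds because of the descriptive fallback. The finding does not show that the pilot is the wrong size, that it needs a multiplicity correction, or that an efficacy claim is planned.

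**What to change.** **Section 1.1 B.** Restate the Aim 2 hypothesis as an objective: assess feasibility, and estimate how the change from Week 0 to Week 7 differs between each intervention group and standard care.

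**Section 6.1.** State that the efficacy outcomes of the interventional phase are exploratory. Report every outcome measured at both Week 0 and Week 7, whatever the size or direction of the result, as a between-group difference in change (TENS vs SC and MM vs SC) with a 95% CI. Apply this to non-normal outcomes too, using a suitable estimate, so that they are not left with within-arm tests alone. State that no efficacy conclusion will be drawn from individual p-values or from changes within an arm.

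**Cost.** Wording in two sections; no new data, visits or participants. The downside is that no individual outcome can be claimed as a confirmed effect, and the intervals will be wide, at about 0.85 SD of the change either side. That width is a property of 12 per arm, and a planner of the later trial needs to see it.

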### 1.2 Research Significance

Anti-retroviral therapy (ART) has increased longevity of PLHIV. However, comorbidities and disability may emerge over time. Chronic pain is common, with prevalence of 39-85%. Chronic pain in PLHIV has a multifactorial etiology. It is associated with increased odds of impaired mobility, self-care, usual activities, and disability. In middle aged and older PLHIV, pain is associated with frailty.

Distal sensory polyneuropathy (DSP) is a common neurological complication of HIV disease, with prevalence exceeding 40%. The etiology is related to HIV-infection, associated metabolic changes, mitochondrial dysfunction, and neurotoxic effects of ART. Risk factors include older age, lower CD4 nadir, and exposure to certain antiretroviral drugs. Symptoms include impaired sensation, paresthesia, diminished reflexes, and pain. In PLHIV and DSP, the prevalence of chronic neuropathic pain is 54-78%. We have found that DSP is associated with worse quality of life, poorer lower extremity function, and more severe disability, and that disability associated with DSP in PLHIV is mediated through pain and depression. Other studies have reported associations between DSP and sleep disturbance, interference with activities and emotions, and greater levels of catastrophizing and depression. Although impairments of gait and balance have been identified in PLHIV, it remains unclear if DSP further affects gait and physical performance.

Management of pain in PLHIV and DSP can include pharmaceutical approaches, but their effectiveness is uncertain. Opioids have poor efficacy for management of chronic pain. The literature on non-pharmaceutical management of DSP in PLHIV is limited to 2 trials of night splints and exercise and a small number of pilot or case studies that have explored yoga, electrical stimulation, or a combination of manual therapy, electrical stimulation, stretching, and self-management.

Mindfulness meditation has been used to reduce stress and symptoms in people with chronic diseases, including HIV. The practice involves bringing one's attention to experiences in the present moment. Mindfulness has been shown to reduce ART side-effects, enhance quality of life, improve emotional status, and improve CD4 cell count in PLHIV. It has not been specifically studied for management of chronic pain in PLHIV and DSP.

Conventional TENS involves low-voltage current applied to the skin for pain relief. High frequency TENS is recommended for patients who are taking opioid pain medication. TENS has been widely studied in patients with chronic pain, although its effectiveness remains uncertain. In patients with

diabetic neuropathy, studies have reported that TENS is effective for reduction in neuropathic symptoms. Other than a double case study using micro-current TENS (a specific form that is not widely used), TENS has not been studied in PLHIV and DSP.

DSP is associated with a wide array of impairments and limitations in PLHIV, but the study of non-pharmaceutical intervention strategies has been sparse. Mindfulness mediation and conventional TENS have not been studied in this population. Current gaps in knowledge include quantification of whether DSP in PLHIV adversely affects gait, balance, physical performance, and physical activity, and identification of interventions to improve clinical outcomes.

### 1.3 Research Design and Methods

This study will include a cross-sectional phase for Aim 1, and an interventional phase with 3 arms for Aim 2. All enrolled participants (those with DSP and those without DSP) will be involved with the cross-sectional phase for Aim 1. Only participants with DSP and foot pain will continue on into the interventional phase for Aim 2. Data will be collected via an array of non-invasive tests and questionnaires that will be administered a members of the study team. All data except for gait and walking endurance will be collected in a private room. Gait and walking endurance measurements will be conducted in a room of adequate size for this, or in a nearby unobstructed hallway.

#### A. Research Procedures

Procedure (in order of occurrence)	When	Where	By Whom
Recruitment of Participants Cross-sectional phase and interventional phase	May 2022-June 2024	various HIV treatment centers in the NJ region and/or HIV support groups	[name] [name] [name]  [name]
Screening for Eligibility Cross-sectional phase and interventional phase	May 2022–June 2024	By phone or HIPAA compliant ZOOM meeting	[name]  [name]
Consenting Cross-sectional phase and interventional phase	May 2022–June 2024	Rutgers study site (in Newark or Voorhees) or Wm Way Center in Philadelphia	[name]  [name]
Baseline Testing (Week 0) Cross-sectional phase and interventional phase	May 2022–June 2024	Rutgers study site (in Newark or Voorhees) or Wm Way Center in Philadelphia for in-person tests and questionnaires Physical activity monitoring done at home	[name] [name] [name]  [name]
Group assignment and instruction in interventions for TENS and MM groups Interventional phase only	May 2022–June 2024	Rutgers study site (in Newark or Voorhees) or Wm Way Center in Philadelphia	[name] [name]  [name]
Home-based Interventions and daily	May 2022–July 2024	Participant's home	Participant

question re: adherence via text message (6 weeks) Interventional phase only			
Post-intervention Testing (Week 7) Interventional phase only	May 2022–July 2024	Rutgers study site (in Newark or Voorhees) or Wm. Way Center in Philadelphia for in-person tests and questionnaires Physical activity monitoring done at home	[name] [name] [name]  [name]
Follow up Questionnaire (Week 15) Interventional Phase only for those who were in TENS or MM groups and enrolled after IRB approval to add follow up questionnaire.	April 2024 – Sept. 2024	Participant's home or location of choice via Email/RedCap	[name]

**Procedures to monitor subjects for safety and minimize risk of harm during testing:** Study staff will follow CDC and Rutgers COVID precautions that are in place at the time (such as wearing a face mask and a face shield) throughout the testing session. Study staff will wash their hands before and after a testing session and sanitize their hands frequently throughout a testing session. All equipment including pens or iPads used for questionnaires will be disinfected both prior to and immediately following a testing session for a given participant. Participants will be scheduled one at a time with no overlap. If more than one participant is scheduled on the same day, there will be a full hour gap between participants to allow time for disinfection of all testing equipment. Participants' appointments will be postponed if they are experiencing symptoms of COVID-19 or are febrile or had a high risk exposure to a COVID infected individual during the week prior to their testing appointment. This will be determined by the PI or study staff calling the participant the day prior to or the morning of their appointment. Prior to testing procedures, participants' resting heart rate, blood pressure, respiratory rate and temperature will be taken. If vital signs values or temperature are outside of acceptable ranges, testing will not proceed on that date. All participants will be required to follow COVID precautions that are in place at the time of testing throughout the testing session. Currently, this includes participants wearing masks throughout the session, sanitizing their hands with hand sanitizer prior to the start of testing and prior to leaving the testing session, and maintaining social distance of at least 6' between study team personnel and participants will be maintained except for when testing procedures require closer proximity. All participants will be guided by and supervised by a study team member throughout all testing procedures. During the balance tests that are included the Short Physical Performance Battery, the PI or his designated study team member will stand adjacent to the participant and provide guarding in case the participants experience a loss of balance. The other test that will require proximity of less than 6' is pain pressure threshold testing. After each test, participants will be asked if they would like to sit and rest before continuing on to the next test. If participants appear to be in any distress or become lightheaded during testing, they will be given the option of lying down on a treatment table or sitting in a chair, and their vital signs will be reassessed.

**Procedures to monitor subjects for safety and minimize risk of harm during the period of home-based interventions:** Participants in the interventional phase will be notified on baseline testing day that they should contact the PI if any problems arise during the 6 week at-home

intervention period. Participants in the TENS will be educated on how to inspect their skin after removing electrodes following a TENS treatment. Because DSP typically causes impaired sensation in the distal extremities TENS electrodes will not be placed on the feet. Rather, the locations will be more proximal at designated points on the lower extremities that have been assessed (on the day of baseline testing) by study personnel to have protective sensation as assessed with a 5.07 gauge (10 gram) Semmes-Weinstein monofilament. Participants in the TENS group who do not have protective sensation over the TENS sites in the legs will NOT be provided with TENS treatment. In addition, participants will be contacted once a week by text message meeting and will be asked if they are experiencing any problems or difficulties with the home-based interventions.

**Randomization:** The cross-sectional phase does not require randomization. For the interventional phase, participants with DSP will be randomly assigned to either the TENS group or the MM group or the standard care group (SC) using a web-based random number generator (<https://www.randomizer.org/>) that will link a group code (TENS, MM, or SC) to a participant's study ID number. Once a participant has been randomized to a group, the matching of the participant's ID number and assigned group will be delivered a study team member in a sealed opaque envelope.

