## C. Study Duration

72-80 participants will be seen one time for testing, followed by 5 days of physical activity monitoring for the cross-sectional phase.

The 36-40 participants without DSP will be engage for approximately one week (baseline testing followed by 5 days of activity monitoring).

The 36-40 participants with DSP-related pain will continue with the interventional phase for 6 weeks (home-based treatment or usual care/control) then return for post-intervention testing at week 7, followed by 5 days of activity monitoring. At week 15, those who were randomized to the

TENS or MM groups will receive a short follow-up questionnaire via email/RedCap. Overall, those with DSP (interventional phase) will be participating for approximately 8 weeks if in the Usual Care Group, or 15 weeks if in the TENS or MM groups (to account for the follow up questionnaire).

The overall duration of the study is expected to be 12 months. Participants will be enrolled on a rolling basis as determined by their availability for test dates and times.

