#### B. Secondary Data Collection: Not applicable.

#### 1.10 Timetable/Schedule of Events

Enrollment will be done in a rolling fashion over several months. The chart below outlines the overall timetable.

Timetable	
Recruitment of Participants Cross-sectional phase and interventional phase	May 2022 – June 2024
Screening for Eligibility Cross-sectional phase and interventional phase	May 2022 – June 2024
Consenting Cross-sectional phase and interventional phase	May 2022 – June 2024
Baseline Testing (Week 0) Cross-sectional phase and interventional phase	May 2022 – June 2024
Group assignment and instruction in interventions Interventional phase only	May 2022 – June 2024
Home-based Interventions (6 week period) Interventional phase only	May 2022 – July 2024
Post-intervention Testing (Week 7) Interventional phase only	May 2022 – July 2024
Follow up questionnaire.	April 2024 – Sept. 2024
Data Analysis	Ongoing over the course of the study through Sept. 2024
Manuscript Preparation and Submission	Sept. 2024 – Jan. 2025

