### 4.3 Number of Subjects

#### A. Total Number of Subjects

Interventional Research Protocol Template (HRP-503a) 1.4.2021

PI: [name]

Protocol Short Title: Neuropathy Walks

Protocol Version Date: v10.0 3.1.2024

IRB ID: Pro2020003234  
 Approval Date: 3/18/2024  
 Expiration Date: 1/23/2025

Number of subjects who are expected to be screened: 160  
 Number of subjects who are expected to be enrolled: 80  
 Number of subjects needed to complete the research procedures: 72

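### Does leaving the type of randomisation list unstated put the planned 12 participants per arm at risk?

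*Combined protocol and SAP*

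**What the plan says.** The only description of allocation is the Randomization paragraph in section 1.3 A. Participants with DSP go to TENS, mindfulness meditation or "the standard care group (SC) using a web-based random number generator". The generator ties a group code to a study ID, and the assignment is passed on in a sealed opaque envelope. No ratio, block size, fixed totals or cap per arm is given.

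Section 1.5 gives the size of the interventional phase as "36 participants (12 participants in each of the 3 groups", with 40 entering it. The allowance for losses is "The expected accrual rate is 90% (drop-out rate of <10" percent. Section 1.3 C gives a range: "The 36-40 participants with DSP-related pain will continue with the interventional phase for 6 weeks". Section 1.1 B expects benefit "in each of the 2 intervention groups (mindfulness meditation; TENS) compared to a standard care group". Section 1.4 says the phase is meant to "generate data on the feasibility and effect sizes of the interventions".

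On timing, section 1.10 lists "Group assignment and instruction in interventions" from May 2022 to June 2024. Section 4.1 B has recruitment at the named centres running to March 2024, and section 4.3 C expects the target to be reached by then. The header reads "Protocol Version Date: v10.0 3.1.2024".

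**The concern.** Twelve per arm is the only basis offered for the size of the interventional phase, and nothing in the allocation paragraph secures it. Sealed envelopes hide the next assignment but do not control arm sizes. Enrolment is rolling, the total may fall anywhere from 36 to 40, and 40 does not divide by 3. If a random number generator is used once per participant, arms of quite different sizes are likely.

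Both interventions are compared with the same standard care group, so a small standard care arm would widen both comparisons. In a study meant to supply effect sizes for a later trial, that would be an avoidable loss. Permuted blocks would cost one sentence and no patients.

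**Working it through.** **The plan's own figures.** 12 × 3 = 36; 36 / 0.90 = 40; 72 / 0.90 = 80. All three agree with section 1.5. There is no alpha, power, standard deviation, effect size or precision target to reproduce.

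**Assumption for what follows.** Each participant is assigned independently with probability 1/3 per arm. The documents do not establish this; it is the unfavourable reading. Arm sizes are then multinomial: P(a, b, c) = N! / (a! b! c!) × (1/3)^N.

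| Quantity | N = 36 | N = 38 | N = 40 |
|---|---|---|---|
| P(every arm has at least 12 randomised) | 2.3% | 12% | 26% |
| P(largest minus smallest arm is 6 or more) | 49% | 52% | 54% |

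**Cost in precision at N = 40.** The variance of a comparison between two arms is proportional to 1/n1 + 1/n2. The benchmark is the average over the three pairs of a 14/13/13 split: [2 × (1/14 + 1/13) + 2/13] / 3 = 0.1502. Under independent draws:

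- the mean variance ratio is 1.057;
- the mean standard error ratio is 1.025;
- the probability that a given comparison has a standard error at least 10% above the benchmark is 14%;
- the probability that it is no worse than the benchmark is 43%.

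Two examples against 12 v 12, where 1/12 + 1/12 = 0.1667: for 9 v 15, √[(1/9 + 1/15) / 0.1667] = 1.03; for 8 v 14, √[(1/8 + 1/14) / 0.1667] = 1.09.

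**What blocks of 3 and 6 (chosen with equal chance) would secure from the start.** The gap between arms never exceeds 2. The probability that every arm has at least 12 randomised is 80% at N = 36, 93% at N = 37, and 100% from N = 38 to 40.

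The 10% allowance suggests that 12 is a number of completers. With 40 randomised and independent dropout, the probability of at least 12 completers in every arm is:

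| Dropout | Independent draws | Blocks of 3 and 6 | Fixed 14/13/13 |
|---|---|---|---|
| 10% | 5% | 32% | 32% |
| 5% | 13% | 71% | 73% |

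**What blocking could still achieve at this version.** From May 2022 to the end of February 2024 is 22 months. Group assignment is scheduled over 26 months (to June 2024), or 23 if recruitment ends in March 2024. With even accrual (an assumption; the number allocated is not given), 40 × 22/26 ≈ 34 or 40 × 22/23 ≈ 38 are already assigned. With those assigned by independent draws and the rest in blocks:

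| Already assigned | P(gap of 6 or more) | P(every arm at least 12) |
|---|---|---|
| 20 | 31% | 43% |
| 34 | 49% | 29% |
| 38 | 54% | 26% |
| 40 (no blocking) | 54% | 26% |

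**The case for a change.** The best case for a change is that the gap is real and cheap to close. No section outside 1.3 A adds a restriction, so a reader cannot tell how the arms were formed or whether equal arms were protected. If assignment has been by independent draws, at least one arm will probably have fewer than 12. Restriction from the start would have raised the chance of 12 completers in every arm from 5% to 32% at 10% dropout, or from 13% to 71% at 5%. Varied, concealed block sizes would keep predictability low in an open-label trial. Lateness limits the gain from blocking, but not the value of saying what was done.

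The gap in the text stands, and so do the figures on their assumption. They do not show that the assumption holds. A generator that links codes to study IDs is just what one would use to prepare a balanced list, and section 1.5 states equal arms as the aim. Nor does any stated property of the study fail at 10 or 11 in an arm: the size is called adequate for feasibility and effect sizes, with no numerical criterion. A small standard care arm widens both comparisons, but a large one narrows both, and the 2.5% average takes in both cases. The disclosure argument concerns how the trial is reported; it does not alter the design or the analysis.

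**Conclusion.** No change to the plan is needed. The allocation paragraph omits the ratio and the type of list, but the intended ratio is clear from section 1.5, and the documents do not show that assignment is unrestricted. If it were, the arms would often be unequal, at an average cost of about 2.5% in standard error at N = 40 and with a 14% chance that a given comparison loses 10% or more. Unequal arms cause no bias here, and the repeated measures analysis in section 6.1 can be run with them. Blocking at this stage would gain about 3 percentage points if 34 of 40 are already assigned, and practically nothing if 38 are. It would gain more if only about 20 were assigned, which the timetable makes unlikely. These figures rest on equal assignment probabilities, even accrual and independent dropout. The method used and the actual arm sizes are facts that the investigators hold and would ordinarily give when they report the trial.
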